3.4.2 Inclusion Criteria

3.4.2.1 Screening Period

Subjects are required to meet all of the inclusion criteria (screening period) presented in [Table 3.4.2-1](#).

Table 3.4.2-1 Inclusion Criteria (Screening Period)	
1	
Patients receiving any of the following oral diuretics (including patients planning to initiate treatment during the run-in period)
 
 • Loop diuretics equivalent to furosemide tablet or fine granules at a dose of 40 mg/day or higher • Concomitant use of a loop diuretic and a thiazide diuretic (including thiazide analogs) at any dose • Concomitant use of a loop diuretic and an aldosterone antagonist or potassium-sparing diuretic agent at any dose 
Note: The types and doses of concomitant diuretics are specified as follow:
 
 a) Loop diuretics equivalent to furosemide tablet or fine granules at a dose of 40 mg/day or higher Bumetanide tablet 1 mg, azosemide tablet 60 mg, and torasemide tablet 8 mg b) Thiazide diuretics (including similar drugs) Hydrochlorothiazide tablet, trichlormethiazide tablet, benzylhydrochlorothiazid tablet, and mefruside tablet c) Aldosterone antagonists or potassium-sparing diuretics Spironolactone tablet/fine granules and triamterene capsules
2	Patients with CHF in whom lower limb edema, pulmonary congestion, or jugular venous distension due to volume overload is present. Patients with pulmonary congestion may be enrolled if pulmonary congestion is confirmed by chest x-ray performed within 14 days prior to informed consent.
3	Male and female patients age of 20 to 85, inclusive, at the time of informed consent
4	Patients who are currently hospitalized or who are able to be hospitalized from the day before the run-in period (on Day -4) until the end of the treatment period

Table 3.4.2-1 Inclusion Criteria (Screening Period)

5	Patients who are capable of taking oral tablets
6	Patients who are capable of giving consent

(Rationale for the inclusion criteria [screening period])

- 1) This criterion is set to enroll patients who have volume overload despite having received diuretics other than vasopressin antagonists.
- 2) Volume overload may be manifested by lower limb edema, pulmonary congestion, jugular venous distension, hepatomegaly, and cardiac third sound. Among these manifestations, lower limb edema, pulmonary congestion, and jugular venous distension are selected as the inclusion criterion, because these symptoms are hardly affected by other factors and were reported by many subjects in a late phase 2 trial (Trial 156-03-001) and a phase 3 trial (Trial 156-06-002) of tolvaptan in patients with CHF.
- 3) Subjects participating in the trial should be adults who are capable of being responsible for their own consent. The upper limit of age is set at 85 years because many patients with CHF are elderly and also based on safety considerations.
- 4) Only patients who are able to be hospitalized will be enrolled to ensure accurate assessments and in view of the safety of subjects.
- 5) This criterion is set because tolvaptan tablet will be used as a comparator.
- 6) This criterion is set to ensure the implantation of an ethically appropriate trial.

3.4.2.2 Run-in Period

To appropriately evaluate the efficacy of the IMPs, only subjects who meet all of the inclusion criteria (run-in period) shown in [Table 3.4.2-2](#) and are judged by the investigator or subinvestigator to be appropriate for an advancement to the treatment period will enter into the treatment period.

Table 3.4.2-2 Inclusion Criteria (Run-in Period)

7	Patients with lower limb edema, jugular venous distension (on Day -1 of the run-in period), or pulmonary congestion (confirmed by chest x-ray during the run-in period)
8	Patients who have received diuretics with no change in dose or regimen during the run-in period
9	Patients with no more than 1.0 kg change in body weight over the 2 days (Day -2 and -1 of the run-in period) prior to initial administration of the IMP

(Rationale for the inclusion criteria [run-in period])

- 7) These symptoms are often seen in association with volume overload and therefore selected as a criterion for enrolling patients with volume overload.
- 8) This criterion is set to enroll patients who still have volume overload despite having received diuretics other than vasopressin antagonists.
- 9) This criterion is set because having stable volume overload is necessary for appropriately evaluating the efficacy of OPC-61815.

3.4.3 Exclusion Criteria

Subjects will be excluded if they meet any of the exclusion criteria in [Table 3.4.3-1](#).

Table 3.4.3-1 Exclusion Criteria	
1	Patients with acute heart failure
2	Patients with mainly noncardiogenic congestive symptoms
3	Patients who are on a ventricular assist device
4	Patients who have any of the following diseases, complications, or conditions: 
 • Suspected hypovolemia • Hypertrophic cardiomyopathy (excluding dilated phase) • Valvular disease with significant valvular stenosis • Hepatic encephalopathy with difficulty in adequate fluid intake
5	Patients who have experienced acute myocardial infarction within 30 days prior to the screening examination
6	Patients with a definite diagnosis of active myocarditis or amyloid cardiomyopathy
7	Patients who have any of the following diseases, complications, or conditions: 
 • Poorly controlled diabetes mellitus • Anuria • Dysuria associated with urinary tract obstruction, calculus, or tumor
8	Patients who have any of the following medical histories: 
 • History of sustained ventricular tachycardia or ventricular fibrillation within 30 days prior to the screening examination (for patients without an implantable cardioverter defibrillator) • History of cerebrovascular disease (excluding asymptomatic cerebral infarction) within 6 months prior to the screening examination • History of hypersensitivity or idiosyncratic reaction to benzodiazepines or benzodiazepine derivatives such as the ingredients of OPC-61815, tolvaptan, mozavaptan hydrochloride, and benazepril hydrochloride
9	Patients who are severely obese (body mass index [BMI] = body weight [kg]/height [m] ² exceeding 35 kg/m ²)
10	Patients with supine systolic blood pressure of <90 mmHg
11	Patients with any of the following abnormalities in laboratory test results: Total bilirubin >3.0 mg/dL, serum creatinine > 3.0 mg/dL, serum Na <125 mEq/L and >147 mEq/L, and serum K >5.5 mEq/L

Table 3.4.3-1 Exclusion Criteria	
12	Patients with current symptoms or a history of hepatic impairment (including patients with aspartate aminotransferase [AST] or alanine aminotransferase [ALT] exceeding 3 times the upper limit of the reference range at the screening examination)
13	Patients who are unable to sense thirst or who have difficulty with fluid intake
14	Female patients who are breast-feeding or who have a positive pregnancy test result prior to receiving IMP
15	Sexually active males or women of childbearing potential (WOCBP) who do not agree to practice birth control or remain abstinent during the trial and for 30 days after the final IMP administration.
16	Patients who have received tolvaptan within 28 days prior to the screening examination
17	Patients who have participated in a clinical trial in which they received OPC-61815
18	Patients who have participated in another clinical trial and received another IMP within 30 days prior to the screening examination
19	Patients who are otherwise judged to be ineligible by the investigator or subinvestigator

Nonchildbearing potential is defined as male and female subjects who are surgically sterile (ie, male subjects who have undergone bilateral orchidectomy and female subjects who have undergone bilateral oophorectomy and/or hysterectomy) and female subjects who have been postmenopausal for at least 12 consecutive months.

Subjects must agree to the restrictions to concomitant medications as described in [Section 4](#).

Subjects who sign an ICF but are not assigned to IMP are permitted to be re-screened one more time. In the event that the screening assessment is repeated, a new ICF signed by the subject must be obtained and a new subject identifier will be assigned to the subject.

[Rationale for the exclusion criteria]	
1	This criterion is set because the rapid onset or worsening of the symptoms may hinder the conduct of the trial.
2	The criterion is set because the proposed target patient population of OPC-61815 is patients who have volume overload associated with CHF.
3	The use of a ventricular assist device may affect the efficacy or safety assessment of the IMPs.
4	Excessive diuretic treatment may adversely affect these symptoms.
5, 6	These criteria are based on safety considerations.
7	This criterion is based on safety considerations and set to exclude patients ineligible for participation in the trial.
8	These criteria are based on safety considerations.
9	This condition may hinder the efficacy assessment of the IMPs.
10	Blood pressure may decrease due to diuresis.

11 to 13	These criteria are based on safety considerations.
14 and 15	These criteria are based on general safety and ethical considerations.
16 and 17	The use of the IMPs may affect the efficacy or safety assessment of the IMPs.
18 and 19	These criteria are based on general safety and ethical considerations.

3.5 Endpoints

3.5.1 Primary Endpoint

Change in body weight from baseline at time of final IMP administration (day after final IMP administration)

[Rationale for the primary endpoint]

Since volume overload occurs at various body sites in CHF patients, body weight (change from baseline) is the most appropriate measure that objectively reflects the diuretic effect of the IMPs on the general state of volume overload. Therefore, the change from baseline in body weight is selected as the primary endpoint as in a phase 3 trial of tolvaptan in patients with CHF (Trial 156-06-002).

3.5.2 Secondary Endpoints

- Congestive symptoms (lower limb edema, pulmonary congestion, jugular venous distension, hepatomegaly, cardiothoracic ratio, pulmonary rales, and cardiac third sound)
- New York Heart Association (NYHA) classification

[Rationale for the secondary endpoints]

Congestive symptoms are measures that reflect volume overload resulting from CHF and therefore selected as a secondary endpoint for evaluating the efficacy of OPC-61815 using tolvaptan tablet as a comparator.

In addition to congestive symptoms, the NYHA classification, which assesses the severity of heart failure based on subjective symptoms is selected as a secondary endpoint to evaluate the efficacy of OPC-61815 using tolvaptan tablet as a comparator.

3.5.3 Pharmacokinetic Endpoint

Plasma concentrations of OPC-61815 free form and tolvaptan (OPC-41061)

3.5.4 Pharmacodynamic Endpoints

Daily urine volume, daily fluid intake, daily fluid balance, serum sodium concentration, serum potassium concentration, serum osmolality, biomarker measurements (plasma concentrations of AVP and brain natriuretic peptide [BNP], plasma renin activity, and serum concentrations of N-terminal pro-brain natriuretic peptide [NT proBNP] and troponin I), daily urine sodium excretion, daily urine potassium excretion, and urine osmolality

3.5.5 Safety Endpoints

Adverse events, clinical laboratory tests (including pregnancy test), physical examination, vital signs (blood pressure, pulse rate, and body temperature), and 12-lead electrocardiography (ECG)

3.6 Measures to Minimize/Avoid Bias

3.6.1 Randomization

Subjects who meet the criteria for a shift to the treatment period will be randomized at a 1:1 ratio to either of the OPC-61815 16-mg injection group or the tolvaptan 15-mg tablet group according to the interactive web response system (IWRS). A randomization confirmation form will be prepared separately to document the detail of the assignment method of treatments to subjects. The date of randomization and the IMP number will be recorded in the eCRF.

3.6.2 Blinding

Prior to start of the trial, the IMP allocation manager and the IMP packer will ensure that the IMPs are indistinguishable from each other. The allocation table will be kept under lock and key until the unblinding to be performed after finalization of all of the eCRFs and the database.

3.7 Trial Procedures

Trial assessment time points are summarized in [Table 3.7-1](#).

Table 3.7-1 Schedule of Assessments

Item	Day	Screening		Run-in Period			Treatment Period					Follow-up
		-7 to -4	-4	-3	-2	-1	1	2	3	4	5	
Informed consent		◊										
Informed consent for DNA storage		○(Optional Participation)										
Subject background		◊										
Inclusion/exclusion criteria		◊				◊						
Confirmation of concomitant medication/therapy		←→										
Subject registration, randomization ^a		◊					●					◊
Hospitalization			←								→	
IMP administration							♦	♦	♦	♦	♦	
Confirmation of IMP compliance							←→					
Plasma drug concentrations							■	●				(◊) ^b
Daily urine volume, daily fluid intake, urine sodium and potassium concentrations, urine osmolality			↔	↔	↔	↔	↔	↔	↔	↔	↔	
Serum sodium ^c and potassium concentrations ^c		◊					●■	●	●	●	●	◊
Serum osmolality, biomarkers ^d							●					●
Body weight		◊		●	●	●	●	●	●	●	●	◊
Congestive symptoms ^e		◊		◊	◊	◊	◊	◊	◊	◊	◊	◊

Table 3.7-1 Schedule of Assessments

Item	Day	Screening		Run-in Period			Treatment Period					Follow-up	
		-7 to -4	-4	-3	-2	-1	1	2	3	4	5		
Chest x-ray (cardiothoracic ratio, pulmonary congestion) ^f		◊		◊ Once during run-in period								◊	
NYHA classification				◊ Once during run-in period								◊	
Adverse events		← →											
Laboratory tests		◊					●					●	◊
Physical examination		◊		◊	◊	◊	◊	◊	◊	◊	◊	◊	◊
Vital signs (Blood pressure, pulse rate, body temperature)		◊		●	●	●	●	●	●	●	●	●	◊
12-Lead ECG ^g		◊				●■		◊				◊	
Urine pregnancy test (WOCBP only)		◊											◊
DNA storage ^h							○						

●= Before breakfast; ♦ = After breakfast; ■ = Predetermined time after IMP administration (see Table 3.7-2); ◊= Feasible time;

○= Optional (subjects at sites with a DNA storage agreement who gave informed consent for DNA storage before start of the trial)

^aSubject registration and randomization: Subject registration and randomization will be performed using IWRS at screening and on Day 1, respectively.

Subjects who meet all of the inclusion criteria and do not fall under any of the exclusion criteria will be assigned to receive IMP administration. In principle, randomization will be performed on Day 1 (if not feasible, randomization on Day -1 is acceptable, but eligibility regarding concomitant diuretics should still be reconfirmed on Day 1). Information on IMP administration and completion or discontinuation (early termination/withdrawal) will be recorded in the IWRS.

^bPlasma drug concentrations will be measured at a feasible time only for early termination/withdrawal.

^cMeasurement of serum sodium and potassium concentrations during the treatment period will be performed at both the central laboratory and the trial site. If it is difficult to perform serum sodium and potassium concentration measurement at the trial site, plasma sodium and potassium concentrations may be

measured. Either serum or plasma should be used consistently for measurement of sodium and potassium concentrations in a given subject. However, even if plasma sodium and potassium concentrations are measured at the trial site, serum sodium and potassium concentrations will be measured at the central laboratory.

^dBiomarkers: Plasma concentrations of AVP, BNP, plasma renin activity, and serum concentrations of NT-proBNP and troponin I

^eCongestive symptoms: Lower limb edema, jugular venous distension, hepatomegaly, pulmonary rales, and cardiac third sound

^fChest x-ray: cardiothoracic ratio and pulmonary congestion

If chest x-ray has been performed at a regular visit prior to participation in the present trial (within 14 days before informed consent), assessment of cardiothoracic ratio and pulmonary congestion at screening may be performed based on that previous chest x-ray without having to perform a new chest x-ray.

^gTiming of 12-lead ECG: Before breakfast and at 1 to 2 hours postdose on Day 1 and at a feasible time at other time points. If the serum potassium concentration at the trial site or the central laboratory is confirmed to exceed 5.5 mEq/L at any time point with no scheduled 12-lead ECG during the treatment period, an additional 12-lead ECG will be performed as an unscheduled examination.

^hDNA storage: In principle, blood sampling for DNA storage will be performed on the day of initial IMP administration (Day 1). Informed consent to DNA storage should be obtained before blood sampling for DNA storage. If blood sample cannot be collected or re-collection is required, blood sampling will be repeated at a feasible time during the trial period.

Table 3.7-2 Allowable Time Window for Examinations/Tests and Blood Sampling After IMP Administration on Day 1	
Item	Timing
Plasma drug concentrations	60 to 75 minutes after start of IMP administration
	4 to 6 hours after start of IMP administration
	8 to 12 hours after start of IMP administration
Serum sodium concentration, serum potassium concentration	4 to 6 hours after start of IMP administration
	8 to 12 hours after start of IMP administration
12-Lead ECG	1 to 2 hours after start of IMP administration
Congestive symptoms	At a feasible time
Adverse events, physical examination	At a feasible time

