1) Pharmacokinetics and Pharmacodynamics

Following a single intravenous administration of OPC-61815 at 2, 4, 8, or 16 mg, the mean C_{max} , AUC_{24h} , AUC_t , and AUC_∞ values of OPC-61815 free form and tolvaptan increased in a dose-dependent manner. The median t_{max} values of OPC-61815 free form and tolvaptan were from 1.03 to 1.04 and 1.48 to 1.76 hours, respectively, and the mean $t_{1/2,z}$ values were from 1.8 to 3.8 hours and 7.4 to 8.6 hours. The mean CL and V_z values of OPC-61815 free form were from 4.29 to 5.50 L/h and 10.5 to 24.7 L, respectively. The mean ratios of AUC_{24h} , AUC_t , and AUC_∞ for tolvaptan to OPC-61815 free form were from 0.846 to 1.42, 0.847 to 1.45, and 0.989 to 1.77, respectively. Repeated intravenous administration of OPC-61815 at 2, 4, 8, or 16 mg once daily for 5 consecutive days resulted in no accumulation of OPC-61815 free form but an approximately 1.2- to 1.4-fold accumulation of tolvaptan. Tolvaptan exposure (C_{max} and AUC_{24h}) on Day 1, which was the primary variable, following single intravenous administration of OPC-61815 at 16 mg was the closest and similar to that following single administration of tolvaptan 15 mg tablet. Tolvaptan accumulated approximately 1.3-fold by repeated administration of tolvaptan 15 mg tablet once daily for 5 consecutive days, which was similar to the accumulation following repeated intravenous administration of OPC-61815 at 16 mg once daily for 5 consecutive days. The pharmacokinetic parameters of metabolites DM-4103 and DM-4107 after a single intravenous administration and repeated intravenous administration of OPC-61815 at 16 mg were similar to those after a

single oral administration and repeated oral administration of tolvaptan 15-mg tablet, respectively.

When OPC-61815 was intravenously administered at 2, 4, 8, or 16 mg once daily for 5 days, the daily urine volume increased from baseline in all dose groups on the day after start of IMP administration and onward.

2) Efficacy and Safety

The changes (mean \pm standard deviation [SD]) in body weight from baseline at time of final IMP administration were -0.6 ± 0.6 kg in the OPC-61815 2-mg group, -1.1 ± 0.8 kg in the OPC-61815 4-mg group, -1.5 ± 1.1 kg in the OPC-61815 8-mg group, -2.1 ± 1.8 kg in the OPC-61815 16-mg group, and -1.7 ± 1.2 kg in the tolvaptan 15-mg tablet group; body weight decreased from baseline in all treatment groups.

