3.7.1.4 Treatment Period (Day 1)

1) Before breakfast

- Serum sodium concentration, serum potassium concentration, serum osmolality, and biomarkers
- Body weight
- Clinical laboratory tests
- Vital signs (blood pressure, pulse rate, and body temperature)
- 12-Lead ECG
- Blood sampling for DNA storage (DNA storage is optional. Informed consent should be obtained before blood sampling for DNA storage.)

2) After breakfast

Subject are required to urinate completely immediately after breakfast, and urine collection and fluid intake measurement will start to assess the following items from the point at which urination immediately before IMP administration has been completed.

- Daily urine volume, daily fluid intake, and daily fluid balance
- Daily urine sodium excretion and daily urine potassium excretion
- Urine osmolality

3) IMP administration

The investigator or subinvestigator will confirm that the subject meets all of the inclusion criteria and falls under none of the exclusion criteria, administer the IMPs to the subject, and enter the status of IMP administration into the IWRS.

4) After IMP administration

The investigator or subinvestigator will conduct the following examinations.

- Blood sampling for measurement of the plasma drug concentrations: 60 to 75 minutes, 4 to 6 hours, and 8 to 12 hours after start of IMP administration
- Serum sodium concentration and serum potassium concentration: 4 to 6 hours and 8 to 12 hours after start of IMP administration
- 12-Lead ECG: 1 to 2 hours after start of IMP administration

5) At a feasible time

- Congestive symptoms (lower limb edema, jugular venous distension, hepatomegaly, pulmonary rales, and cardiac third sound)
- Adverse events, physical examination
- Concomitant medications and therapies
- Confirmation of IMP compliance

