3.7.1.7 Treatment Period (Days 4 and 5)

1) Before breakfast

- Serum sodium concentration and sodium potassium concentration
- Body weight
- Vital signs (blood pressure, pulse rate, and body temperature)

2) After breakfast

Subject are required to urinate completely immediately after breakfast, and urine collection and fluid intake measurement will start to assess the following items from the point at which urination immediately before IMP administration has been completed.

- Daily urine volume, daily fluid intake, and daily fluid balance
- Daily urine sodium excretion and daily urine potassium excretion
- Urine osmolality

3) IMP administration

4) At a feasible time on each day

- Congestive symptoms (lower limb edema, jugular venous distension, hepatomegaly, pulmonary rales, and cardiac third sound)
- Adverse events, physical examination
- Concomitant medications and therapies
- Confirmation of IMP compliance

3.7.1.8 Treatment Period (Completion Assessment on Day 6 or Withdrawal Assessment on Day After the Final IMP Administration)

The investigator or subinvestigator will conduct the completion assessment on Day 6 as described below. If IMP treatment is discontinued before Day 6 for any reason, the same assessment as the completion assessment for Day 6 will be conducted at a feasible time as the withdrawal assessment on day after final IMP administration, whenever possible, and then follow-up will be made 7 to 10 days after the final IMP administration. During the withdrawal assessment, plasma drug concentrations will be measured (at a feasible time), whenever possible. Information on trial completion or trial withdrawal will be entered into the IWRS.

1) Before breakfast

- Serum sodium concentration, serum potassium concentration, serum osmolality, and biomarkers
- Body weight
- Clinical laboratory tests and vital signs (blood pressure, pulse rate, and body temperature)

2) At a feasible time

- Blood sampling for measurements of plasma drug concentrations (only at the withdrawal assessment)

- Congestive symptoms (lower limb edema, jugular venous distension, hepatomegaly, pulmonary rales, and cardiac third sound)
- Chest x-ray (cardiothoracic ratio and pulmonary congestion)
- NYHA classification
- Adverse events, physical examination
- 12-Lead ECG
- Concomitant medications and therapies

3.7.1.9 Follow-up After Completion of the Treatment Period (Day 12 to Day 15, 7 to 10 Days After the Final IMP Administration)

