3.7.5 Pharmacokinetic, Pharmacodynamic, and Pharmacogenomic Assessments

3.7.5.1 Pharmacokinetic Assessments

3.7.5.1.1 Pharmacokinetic Blood Samples

1) Time points of blood sampling

- Day 1 of the treatment period: 60 to 75 minutes, 4 to 6 hours, and 8 to 12 hours after start of IMP administration
- Day 2 of the treatment period: 22 to 24 hours after start of IMP administration on Day 1 (before IMP administration on Day 2)

2) Procedures for blood sampling and measurements

The central laboratory will collect the blood samples, which will be shipped to the bioanalytical laboratory for analysis. For the handling and shipment of samples, see [Appendix 1](#).

The bioanalytical laboratory will measure the plasma concentrations of OPC-61815 free form and tolvaptan (OPC-41061), report blinded measurement results to the sponsor, if necessary, and provide an electronic file containing unblinded drug concentration data to the sponsor after breaking the blind.

The status (collected/not collected), type (venous or arterial), and date and time of blood sampling will be recorded in the eCRF. The results of drug concentration measurements will be directly reported to the sponsor from the bioanalytical laboratory; therefore, entry in the eCRF will be unnecessary.

In the event that new information on the IMPs is obtained, metabolites that are not specified in this protocol may be analyzed. In addition, the collected plasma samples may be used for investigation of an analytical method, if necessary.

3) Rationale for the timing of blood sampling

In this trial, plasma drug concentration data will be collected to conduct a population pharmacokinetic (PPK) analysis in patients with CHF. The timing of blood sampling for drug concentration measurement is determined based on the results of a

simulation from a PPK model using the results of a phase 2 clinical pharmacology trial of OPC-61815 (Trial 263-102-00001), also considering feasibility. As a result, blood sampling for drug concentration measurements on Day 1 of the treatment period will be conducted at the following 4 time points: a point around which the plasma concentrations of OPC-61815 free form and tolvaptan are expected to reach a peak (60 to 75 minutes after start of IMP administration), and 3 points which are expected to be the elimination phase (4 to 6 hours, 8 to 12 hours, and 22 to 24 hours after start of IMP administration).

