7.6.4 Electrocardiogram Data

For 12-lead ECG parameters, measured values and changes from baseline at each time point and at the time of final IMP administration will be summarized using descriptive statistics.

The numbers and percentages of subjects who have a QTc interval (QTcF) of >450 , >480 , or > 500 msec at any post-treatment time point until the time of final IMP administration will be calculated. The numbers and percentages of subjects who have a change in QTc interval from baseline of >30 and >60 msec at any post-treatment time point and at the time of final IMP administration will be calculated. Also at baseline and at each post-treatment time point, the numbers and percentages of subjects will be calculated in the same manner as described above.

Shift tables for QTcF interpretation (normal or abnormal) will be prepared at each post-treatment time point and at the time of final IMP administration compared with baseline.

8 Management of Investigational Medicinal Product

For full details on IMP management, see the OPC-61815 IB and the clinical operation manual.

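### The Day 3 ECG has no time window relative to dosing, so no scheduled ECG is tied to the tolvaptan peak after repeated dosing

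*Protocol*

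**What the plan says.** The rule for ECG timing, in note g to Protocol Table 3.7-1, is "Before breakfast and at 1 to 2 hours postdose on Day 1 and at a feasible time at other time points". Protocol 3.7.1.4 repeats the one postdose window: "12-Lead ECG: 1 to 2 hours after start of IMP administration". Table 3.7-2, which sets the postdose windows, covers Day 1 only.

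Protocol 3.7.1.6 lists the Day 3 ECG among the items that may be done at any convenient hour. No ECG is listed for Days 2, 4 or 5. The completion ECG (Protocol 3.7.1.8) also has no set hour and falls on Day 6, the day after the last dose.

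For the analysis, Protocol 7.6.4 says that "measured values and changes from baseline at each time point and at the time of final IMP administration will be summarized using descriptive statistics". It adds counts of subjects above 450, 480 and 500 msec, and with rises above 30 and 60 msec, both for any post-treatment time point and for each time point. SAP 9.6 follows the same scheme by nominal time point.

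The phase 2 pharmacokinetics in Protocol 1.2.2 report, for the infusion, "no accumulation of OPC-61815 free form but an approximately 1.2- to 1.4-fold accumulation of tolvaptan". The tablet accumulated about 1.3-fold.

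**The concern.** The Day 1 window covers the median times to peak from phase 2 for both OPC-61815 free form and tolvaptan, so the plan already has an ECG placed near peak. That ECG follows the first dose, before any tolvaptan has accumulated. The later ECG on a dosing day may be taken before the infusion at one site, soon after it at another and in the evening at a third. All these readings enter one Day 3 summary.

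What is at stake is how the Day 3 QTcF results can be read. If tolvaptan had a concentration-related effect on QTcF, low-exposure recordings would dilute it at Day 3, by an amount that depends on site habits.

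The rest of the plan does little to recover the information:

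- The last scheduled plasma sample is "22 to 24 hours after start of IMP administration on Day 1 (before IMP administration on Day 2", and Protocol 6.4 plans no exposure-response analysis.
- Protocol 3.7.3.4 has sites enter the ECG date in the eCRF but does not list the clock time.
- SAP 3.4 leaves unscheduled values out of summaries, so the extra ECGs triggered by high potassium do not contribute.
- SAP 5.5 carries the last available value forward for safety data, so an untimed Day 3 ECG can stand in for a missing final one.

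**Working it through.** The plan states no figure on this point, so there is none to reproduce. The check compares the schedule with the protocol's own pharmacokinetics and then sizes the dilution.

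**Inputs (Protocol 1.2.2, infusion only).** Median time to peak: "values of OPC-61815 free form and tolvaptan were from 1.03 to 1.04 and 1.48 to 1.76 hours". Mean terminal half-life, in the same order: "values were from 1.8 to 3.8 hours and 7.4 to 8.6 hours". Doses are 24 h apart.

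**Step 1: does the Day 1 window cover the peak?** The window is 1 to 2 h. Both 1.03–1.04 h (free form) and 1.48–1.76 h (tolvaptan) lie inside it.

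**Step 2: exposure at a predose Day 3 ECG.** Assume single-exponential decline for about 22 h after the Day 2 peak (24 h less a time to peak of about 2 h). The fraction of peak left is 2^(−22/t½):

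- t½ = 7.4 h: 2^(−22/7.4) = 0.13
- t½ = 8.6 h: 2^(−22/8.6) = 0.17

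The Day 6 ECG, about a day after the last dose, sits at a similarly low level.

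**Step 3: how much of a concentration-proportional effect is lost at Day 3?** The documents do not say when sites record, so two patterns are assumed.

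*Pattern A: half predose, half at peak.* Loss = (1 − f)/2, with f from step 2.

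- f = 0.13: (1 − 0.13)/2 = 0.435
- f = 0.17: (1 − 0.17)/2 = 0.415

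The loss is about 42–44%.

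*Pattern B: recordings spread evenly after the start of dosing.* The model has one compartment and first-order input. C(t) is proportional to the sum over i = 0, 1, 2 of [exp(−k(t+24i)) − exp(−ka(t+24i))], with k = ln 2/t½ and ka chosen so that the peak falls at 1.6 h.

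| Day 3 ECG window | Mean concentration as share of peak (t½ 7.4 h; 8.6 h) | Loss |
|---|---|---|
| 0–8 h | 0.785; 0.807 | 19–22% |
| 0–10 h | 0.733; 0.760 | 24–27% |
| 1–2 h | 0.991; 0.992 | about 1% |

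Under pattern B only 1/8 to 1/10 of the recordings (about 10–13%) would fall within 1 to 2 h.

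**Step 4: how much higher is the peak that no scheduled ECG is tied to?** The 1.2- to 1.4-fold figure is for five daily doses. The documents give no factor for Day 3. The half-lives alone imply, by the third dose, 1 + 2^(−24/t½) + 2^(−48/t½) = 1.12 (7.4 h) to 1.17 (8.6 h). This simple model also falls short of the stated range at steady state, where it gives 1.12–1.17, so it is a rough guide. The increment at Day 3 is probably somewhat below 20–40%.

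**The case against.** The strongest reply is that the gap is narrow.

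- **The new molecule is covered.** OPC-61815 free form does not accumulate, and the Day 1 window contains its peak. What goes unobserved is only the accumulated part of tolvaptan, which is also the active comparator and accumulates similarly in both arms. This stands and limits the point to tolvaptan.
- **Some high exposures are seen on Day 1.** In Protocol Table 2.2-1 the Day 1 tolvaptan Cmax after 16 mg intravenously is 282 ± 96 ng/mL. Applying 1.2 to 1.4 gives 338 to 395 ng/mL, which is (338 − 282)/96 = 0.6 to (395 − 282)/96 = 1.2 SD above the Day 1 mean. Some subjects will therefore reach such levels after the first dose. This also stands.
- **The ECG analysis is descriptive.** It has no hypothesis or margin, and dosing is double-blind with a double dummy, so nothing suggests that timing would differ between arms. The issue is dilution, not bias in favour of one arm.
- **Clock times may exist.** Dose start times are recorded (Protocol 3.2.1), and ECGs reach the sponsor as a central electronic file (Protocol 3.7.3.4). The documents do not say whether that file holds the time, and no analysis by time since dose is planned, so this reply is only potential.
- **The 1 to 2 h window is shown to be peak for the infusion only.** The documents give no time to peak or half-life for the tablet. This stands as a limit on the fix.

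A reader might infer that all the QTcF threshold counts hang on site timing. They do not: the any-time counts include the Day 1 ECG taken near peak. A reader might also infer that about half of any Day 3 effect is lost. Even the half-predose pattern gives 42–44%, no document supports that pattern, and a spread over 8 to 10 h gives 19–27%.

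**Conclusion.** The point holds in limited form. Day 3 is the only scheduled ECG on a dosing day after the first dose, its hour is free, and no scheduled ECG is tied to the tolvaptan peak after repeated dosing. Day 3 QTcF can therefore mix recordings from about 13–17% of peak up to peak. The actual mix depends on site practice.

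Affected are the Day 3 mean change, the Day 3 threshold counts and the Day 3 contribution to the any-time counts. The Day 1 contribution is not affected. The loss of a concentration-proportional tolvaptan effect at Day 3 would run from about 19–27% to about 42–44% under the two assumed patterns. These figures rest on infusion half-lives and a simple model; for the tablet arm they are an extrapolation. The documents give no QT effect size for either drug, so no bias in msec can be computed, and nothing here shows that such an effect exists.

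This is a cheap improvement to a descriptive safety assessment. It does not touch the primary analysis.

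**What to change.** In note g to Protocol Table 3.7-1, in Table 3.7-2 and in Protocol 3.7.1.6, set the Day 3 ECG at 1 to 2 h after the start of IMP administration, as on Day 1. In Protocol 7.6.4 and SAP 9.6, label the Day 3 QTcF results with that window.

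The number of ECGs and the equipment stay the same, and subjects are already in hospital through Day 6, so no visit is added. There are two costs. Sites lose the free choice of hour on Day 3. The documents also support the window as near peak only for the infusion, so the report should not call it the peak for the tablet arm. Even so, a common window makes Day 3 comparable with Day 1 within each arm.
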